8.2.1.2.2. Pulse oximetry

Measurement of blood oxygen saturation by trained site personnel, using pulse oximeters provided by GSK, is strongly preferred. The SPM presents additional information about GSK-provided pulse oximeters and their use.

8.2.2. Procedures for infant subjects**8.2.2.1. Demographic data and lifestyle characteristics**

Demographic data may include (but are not limited to) geographic ancestry (race)*, ethnicity*, month of birth (if allowed per local regulation) and year of birth.

Lifestyle characteristics may include but are not limited to living environment, household composition, breastfeeding (breastfeeding only / breastfeeding with supplementation / no breastfeeding), passive smoking, and extent of contact with children less than 6 years of age.

*Refer to Section [8.2.1.1.1](#) for additional information about collection of geographic ancestry (race) and ethnicity.

CONFIDENTIAL209544 (RSV MAT-004)
Protocol Amendment 3 Final**8.2.2.2. Physical examination at Visits 1-NB through 5-NB**

A physical examination will be performed at each protocol-specified visit (Visits 1-NB through 5-NB).

The examination will include (but need not be limited to) assessment of the following:

- Weight, length, head circumference
- Temperature, heart rate and respiratory rate.
- Age-appropriate organ system examination including (but not limited to): eyes, ears, musculoskeletal, pulmonary (chest auscultation), cardiovascular, neurological and genitourinary.
- Presence of congenital anomalies.

8.2.3. Study holding rules and safety monitoring**8.2.3.1. Limitation on number of doses administered per day (first 30 maternal subjects)**

Dosing will be limited to 10 maternal subjects per day across all sites until the first 30 maternal subjects have been dosed. During this period, within any given study site, subjects will be dosed sequentially and at least 60 minutes apart.

Additional enrolment and dosing may not proceed without written authorization. After this authorization has been provided, enrolment and dosing may continue without limitation on the number of subjects dosed per day or the time between consecutive subjects dosed at a given study site.

As noted in Section 6.1, all (up to 300) maternal subjects must be closely observed at the study site for at least 60 minutes after dose administration.

8.2.3.2. Outcomes of safety evaluations

Safety evaluations will include those performed by investigators, by a blinded safety review team (SRT) composed of GSK RSV team members, and by an unblinded, independent data monitoring committee external to GSK (IDMC). **Details** regarding SRT and IDMC safety evaluations **are provided in a separate IDMC charter.**

- If no safety signal is observed after the first 30 maternal subjects have been enrolled and dosed, this will be documented. GSK will provide investigators with written authorization to enroll and dose the remaining ~ 270 maternal subjects.
- If the IDMC's decision(s) after a safety evaluation require(s) them to take some action (e.g., to suspend, modify, or continue the conduct of the study for all groups or for selected groups), the IDMC Chair (or his/her representative) will notify the study CRDL. The study CRDL will be accountable for notifying investigators in writing of the IDMC's decision(s).

CONFIDENTIAL209544 (RSV MAT-004)
Protocol Amendment 3 Final**8.2.3.3. Study holding rules****8.2.3.3.1. Holding rules assessed by the investigator**

The investigator and /or designees will assess on an ongoing basis whether any of the holding rules in [Table 17](#) have been met, irrespective of the number of subjects enrolled and/or timing of the event relative to dosing.

Table 17 Holding rules assessed by the investigator

| Holding Rule | Event | Number of mothers/infants |
|--------------|--|---------------------------|
| 1a | Maternal death or any life-threatening SAE , or fetal death or unexplained neonatal/infant death up to 1 year of age | ≥ 1 |
| 1b | Any non-life-threatening SAE that cannot be reasonably attributed to a cause other than vaccination (applies to both maternal subjects and infants of vaccinated mothers). | ≥ 1 |
| 1c | Any withdrawal from the study (by the investigator or subject request) following a Grade 3 AE that cannot reasonably be attributed to a cause other than vaccination. | ≥ 1 |
| 1d | Any solicited administration site or systemic event leading to hospitalization , or fever > 40°C (104°F) (oral route) or necrosis at the injection site, within the 7-days (Day 1-7) post-vaccination period. | ≥ 1 |

If the investigator becomes aware of a holding rule (e.g., 1a-1d in [Table 17](#)) being met, he/she will suspend enrolment and study vaccine/product administration and inform GSK as soon as possible (no later than within 24 hours).

The investigator is not permitted to start the administration of the next dose or enrol additional subjects until provided with written documentation of the favourable outcome of the safety evaluation, and written authorization to proceed.

Refer to [Table 23](#) for contact information.

The below flow of communication must be followed.

- Investigator (or a designee) informs their local sponsor contact as soon as possible (no later than within 24 hours). ([Table 23](#)).
- The local sponsor contact informs the central sponsor contact (e.g., the SDL; the CRDL) as soon as possible (no later than within 24 hours).
- The central sponsor team ensures that SBIR is blocked, all sites administering study vaccine/product are informed, and all country or region- specific regulatory authorities are informed.
- Study sites confirm that they have been notified and have taken appropriate action, providing appropriate documentation to their local sponsor contact.
- The GSK Vaccine Safety Monitoring Board evaluates the case after receipt of the IDMC's recommendations / and takes the decision to stop or to restart dose administration.

CONFIDENTIAL209544 (RSV MAT-004)
Protocol Amendment 3 Final

- Where required per local / regional regulation, the central sponsor team submits a substantial amendment to the local/regional authority requesting authorization to re-start the study.
- When all required authorizations to re-start the study in a country / region have been provided, the central sponsor team provides written notification to local sponsor contacts; local sponsor contacts then provide written notification to study sites.

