| Pre-vaccination body temperature | | • | | | | | | | | | | | Preferred location for measurement will be the oral cavity. "Fever" = temperature ≥38.0°C/100.4°F regardless of the location of measurement. | |
| Urine sample | • | • | • | • | • | | | | | | | | Table 11 | |

CONFIDENTIAL

209544 (RSV MAT-004)
Protocol Amendment 3 Final

| Epochs | Epoch 001 | Epoch 002 | | | | | | | | | | Additional Information | | |
|---|------------|---------------------------------------|--|-----|-----|---------------|--|---------|---------|------------------|---------------------|------------------------|--|--|
| | | | May be replaced by V5, depending on delivery date | | | | To coincide with infant visits 2-NB, 3-NB, 4-NB | | | | Event Driven | | | |
| Visit / Contact | Screening | V1 | V2 | V3 | V4 | V5 | V6 | V7 | V8 | Monthly contacts | Safety Visit | MA-RTI Visit | For monthly contacts: Table 2 & Section 8.4.2. After delivery, maternal & infant monthly contacts coincide. | |
| Gestational Age (GA) | | 28 ^{0/7} - 33 ^{6/7} | | | | | | | | | | | | |
| Visit Day | D-28 – D-1 | D1 | D8 | D31 | D61 | Delivery D1PD | D43 PD | D121 PD | D181 PD | | | | | |
| Blood sample (hematology / biochemistry, ~ 5.5 ml) | • | • | • | | | | | | | | • | | Table 11 If screening sample ≤ 15 days before V1, then V1 sample not required. During an event-driven safety visit, additional samples are per investigator's discretion and standard of care and to be tested locally. | |
| Blood sample (hematocrit: ~ 3.0 ml) | | | | • | | • | • | | | | | | Table 11 | |
| Blood sample (immunogenicity ~ 10 ml) | | • | | • | | • | • | | | | | | | |
| Cord blood (~ 5 to 10 ml) | | | | | | • | | | | | | | | |
| Nasal swab | | | | | | | | | | | | • | | |
| Check contraindications to and criteria for temporary delay for vaccination | | 0 | | | | | | | | | | | Sections 5.2.1 and 7.1.1 | |

CONFIDENTIAL

209544 (RSV MAT-004)
Protocol Amendment 3 Final

| Epochs | Epoch 001 | Epoch 002 | | | | | | | | | | Additional Information | | |
|--|------------|---------------------------------------|---|-----|-----|---------------|--------|--|---------|------------------|--------------|------------------------|--|--|
| | | | May be replaced by V5, depending on delivery date | | | | | To coincide with infant visits 2-NB, 3-NB, 4-NB | | | | | Event Driven | |

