7.3. Lost to follow-up

A subject will be considered lost to follow-up if he or she fails to return for scheduled visits and is unable to be contacted by the study site.

Please refer to the SPM for a description of the actions to be taken before considering the subject as lost to follow-up.

**8. STUDY ASSESSMENTS AND PROCEDURES
(AMENDED 30-SEP-2020)**

Study procedures and their timing are summarised in the SoAs (Section 1.3). Information not provided in the SoAs follows.

Readers are reminded that study visits /contacts, assessments and procedures *do not* replace local standards of care, and that any adverse event / potential adverse event identified during a study visit/contact or procedure should be treated according to local medical practice or by referral to an appropriate health care provider.

Adherence to the protocol is essential and required for study conduct.

Protocol waivers or exemptions are not allowed unless necessary for the management of immediate safety concerns.

The investigator is not allowed to do testing on samples outside of what has been agreed upon by the IEC/IRB.

Immediate safety concerns should be discussed with the sponsor as soon as they occur or when the study team is aware of them.

All screening evaluations must be completed and the results reviewed before confirming that potential subjects meet all eligibility criteria.

The investigator will maintain a screening log of all subjects screened. All relevant information, such as confirmation of eligibility and reasons for screening failure will be mentioned in this screening log.

Procedures conducted as part of routine clinical management (e.g. hematologic profiles) and obtained before the subject signed the Informed Consent Form (ICF) may be used for screening and/or for establishing a clinical baseline, provided the procedure met protocol-specified criteria and was performed within the time frame defined in the SoA (Section 1.3).

The SPM provides the investigator and site personnel with administrative and detailed technical information that does not impact subject safety.

CONFIDENTIAL209544 (RSV MAT-004)
Protocol Amendment 3 Final

Study Procedures During Special Circumstances: COVID-19 pandemic

- During special circumstances (e.g., the COVID-19 pandemic), the specific guidance from local public health and other competent authorities regarding the protection of individuals' welfare must be applied.

For the duration of such special circumstances:

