| d. | Results in disability/incapacity Note: The term disability means a substantial disruption of a person’s ability to conduct normal life functions. This definition is not intended to include experiences of relatively minor medical significance such as uncomplicated headache, nausea, vomiting, diarrhoea, influenza like illness, and accidental trauma (e.g. sprained ankle) which may interfere or prevent everyday life functions but do not constitute a substantial disruption. |
| e. | Is a congenital anomaly/birth defect in the offspring of a study participant |
| f. | Abnormal pregnancy outcomes (e.g. spontaneous abortion, foetal death, stillbirth, congenital anomalies, ectopic pregnancy). |
| g. | Other situations Medical or scientific judgement should be exercised in deciding whether reporting is appropriate in other situations, such as important medical events that may not be immediately life-threatening or result in death or hospitalisation but may jeopardise the participant or may require medical or surgical intervention to prevent one of the other outcomes listed in the above definition. These should also be considered serious. Examples of such events are invasive or malignant cancers, intensive treatment in an emergency room or at home for allergic bronchospasm, blood dyscrasias or convulsions that do not result in hospitalisation. |

CONFIDENTIAL209544 (RSV MAT-004)
Protocol Amendment 3 Final**10.3.3. Solicited events****a. Solicited administration site events**

The following administration site events will be solicited:

Table 27 Solicited administration site events

| All age groups |
|----------------|
| Pain |
| Redness |
| Swelling |

b. Solicited systemic events

The following systemic events will be solicited:

Table 28 Solicited systemic events

| Adult/Child (≥ 6 years) |
|-------------------------------|
| Fatigue |
| Fever |
| Nausea |
| Vomiting |
| Diarrhea |
| Abdominal pain |
| Headache |

Note: maternal subjects will be instructed to measure and record the (preferably) oral temperature at least once each day, at approximately the same time each day. Should additional temperature measurements be performed at other times of day, subjects will be instructed to record the highest temperature in the electronic Subject Diary (e-Diary).

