10.3.9. Assessment of intensity and toxicity**10.3.9.1. Assessment of intensity**

The intensity of the following solicited events will be assessed as described:

Table 29 Intensity scales for solicited symptoms in adults

| Adults/Child (≥6 years) | | |
|----------------------------|-----------------|---|
| Adverse Event | Intensity grade | Parameter |
| Pain at injection site | 0 | None |
| | 1 | Mild: Any pain neither interfering with nor preventing normal every day activities. |
| | 2 | Moderate: Painful when limb is moved and interferes with every day activities. |
| | 3 | Severe: Significant pain at rest. Prevents normal every day activities. |
| Redness at injection site | | Record greatest surface diameter in mm |
| Swelling at injection site | | Record greatest surface diameter in mm |
| Temperature* | | Record temperature in °C/°F (with 1 decimal) Temperature will be analysed in 0.5°C increments from ≥ 38.0°C /100.4°F) Grade 3 fever is defined as > 39.0°C /102.2°F |
| Headache | | |
| Fatigue | 0 | Normal |
| Nausea | 1 | Mild: Easily tolerated |
| Vomiting | 2 | Moderate: Interferes with normal activity |
| Diarrhea | 3 | Severe: Prevents normal activity |
| Abdominal pain | | |

*Refer to the SoA for the definition of fever and the preferred location for temperature measurement.

The maximum intensity of local injection site redness/swelling will be scored at GSK Biologicals as follows:

| | | |
|---|---|---------------------|
| 0 | : | ≤ 20 mm |
| 1 | : | > 20 mm to ≤ 50 mm |
| 2 | : | > 50 mm to ≤ 100 mm |
| 3 | : | > 100 mm |

The investigator will assess the maximum intensity that occurred over the duration of the event for all unsolicited AEs (including SAEs) recorded during the study. The assessment will be based on the investigator's clinical judgement.

CONFIDENTIAL209544 (RSV MAT-004)
Protocol Amendment 3 Final

The intensity should be assigned to 1 of the following categories:

- 1 (mild) = An AE which is easily tolerated by the subject, causing minimal discomfort and not interfering with everyday activities.
- 2 (moderate) = An AE which is sufficiently discomforting to interfere with normal everyday activities.
- 3 (severe) = An AE which prevents normal, everyday activities
(In adults/adolescents, such an AE would, for example, prevent attendance at work/school and would necessitate the administration of corrective therapy.)

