10.3.9.2. Assessment of causality

All solicited administration site and systemic events will be considered causally related to vaccination. The complete list of these events is provided in [Table 27](#) and [Table 28](#).

The investigator must assess the relationship between study vaccine(s)/product(s) and the occurrence of each unsolicited AE/SAE using clinical judgement. Where several different vaccines/products were administered, the investigator should specify, when possible, if the unsolicited AE/SAE could be causally related to a specific vaccine/product (i.e. investigational, control/placebo or co-administered vaccine). When causal relationship to a specific vaccine(s)/product(s) cannot be determined, the investigator should indicate the unsolicited AE/SAE to be related to all products.

Alternative plausible causes, such as natural history of the underlying diseases, concomitant therapy, other risk factors, and the temporal relationship of the event to the study vaccine(s)/product(s) will be considered and investigated. The investigator will also consult the IB to determine his/her assessment.

Causality should be assessed by the investigator using the following question:

Is there a reasonable possibility that the unsolicited AE may have been caused by the study vaccine/product?

- YES : There is a reasonable possibility that the study vaccine(s)/product(s) contributed to the AE.
- NO : There is no reasonable possibility that the AE is causally related to the administration of the study vaccine(s)/product(s). There are other, more likely causes and administration of the study vaccine(s)/product(s) is not suspected to have contributed to the AE.

If an event meets the criteria to be determined as ‘serious’ (see Section [10.3.2](#)), additional examinations/tests will be performed by the investigator to determine ALL possible contributing factors for each SAE.

CONFIDENTIAL209544 (RSV MAT-004)
Protocol Amendment 3 Final

Possible contributing factors include:

- Medical history.
- Other medication.
- Protocol required procedure.
- Other procedure not required by the protocol.
- Lack of efficacy of the vaccine(s)/product(s), if applicable.
- Erroneous administration.
- Other cause (specify).

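### Holding rule 1d counts a fever above 40°C only by the oral route, although other routes are permitted, so an isolated non-oral reading does not literally trigger the automatic hold

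*Protocol*

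**What the plan says.** Table 17 in Section 8.2.3.3.1 lists the rules that an investigator applies continuously and that each need one subject. Rule 1d covers Days 1 to 7. It is met by a solicited event leading to hospitalization, or by "fever > 40°C (104°F) (oral route) or necrosis at the injection site". When it is met, the investigator suspends enrolment and dosing and informs the sponsor within 24 hours.

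The other provisions on maternal temperature are not restricted to one route:

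- Section 10.3.3: "maternal subjects will be instructed to measure and record the (preferably) oral temperature at least once each day". If more readings are taken on a day, "subjects will be instructed to record the highest temperature in the electronic Subject Diary", with no condition on route.
- Table 29 (Section 10.3.9.1) sets Grade 3 fever at above 39.0°C without a route. Its footnote says: "Refer to the SoA for the definition of fever and the preferred location for temperature measurement".
- That definition, in the pre-vaccination temperature row of Table 1, is 38.0°C or more "regardless of the location of measurement", with the mouth as the preferred site.
- Section 7.1.1, on delaying vaccination, accepts any age-appropriate route and again prefers oral.

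**The concern.** The fever limb of rule 1d is an objective stop. One very high temperature halts dosing without anyone having to judge seriousness, in the first trial of this vaccine in pregnant women. The data feeding the rule come from a diary that permits non-oral readings, while the trigger names only oral ones. A permitted reading of, say, 40.5°C taken elsewhere is a fever, is Grade 3, and would count toward rule 2b if it lasted 48 hours. On the words of the table it still does not meet the fever limb of 1d. Two sites could therefore treat the same reading differently: one stops dosing everywhere and the other continues.

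**Working it through.** The point rests on text, and the Protocol gives no figure to reproduce. The test case is one maternal subject with a single non-oral reading above 40°C in Days 1 to 7 who is not hospitalized, not judged to have a serious event and not withdrawn. Each numbered rule is applied in turn.

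| Rule | What it needs | Met? |
|---|---|---|
| 1a | Death or a life-threatening SAE | No |
| 1b | Another SAE with no reasonable cause but vaccination | No, not judged serious |
| 1c | Withdrawal after a Grade 3 AE with no reasonable other cause | No, not withdrawn |
| 1d, hospitalization | Solicited event leading to hospitalization, any route | No |
| 1d, fever | Above 40°C, oral | No, on the literal wording |
| 1d, necrosis | Injection-site necrosis | No |
| 2b | Grade 3 systemic event lasting 48 h or more, in at least 4 subjects and at least 25% of active recipients | No, one subject |

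No automatic hold follows. For comparison of trigger size, with the 16 active recipients used in Section 8.2.3.4, rule 2b needs max(4, 0.25 × 16) = 4 subjects, against 1 for rule 1d.

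Changing any one condition restores a single-subject route. Hospitalization meets 1d whatever the thermometer site. A judgement of seriousness opens 1a or 1b, and on attribution Section 10.3.9.2 says: "All solicited administration site and systemic events will be considered causally related to vaccination". Withdrawal can meet 1c, because a fever above 40°C exceeds the 39.0°C limit for Grade 3.

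**Size.** Let p be the rate of fever above 40°C and q the share of such readings taken orally. Among n recipients, the chance of at least one qualifying reading is 1 − (1 − p)^n if any route counts and 1 − (1 − pq)^n if only oral counts. The Protocol gives neither p nor q. The following is therefore illustration only, with n = 16 and p set to the 1% and 10% that Section 8.2.3.4 uses as reference rates for rules 1a to 1c:

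| Assumed p | Any route | Oral only, q = 90% | q = 80% | q = 50% |
|---|---|---|---|---|
| 1% | 0.149 | 0.135 | 0.121 | 0.077 |
| 10% | 0.815 | 0.779 | 0.737 | 0.560 |

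The differences overstate the loss, because they treat every non-oral reading as having no other way to a hold. Neither p nor q should be read as an estimate.

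**The case against.** The best defence is that nothing here is contradictory. The definition in Table 1 concerns fever from 38.0°C, and a protocol may define fever by any route yet fix a stricter stopping limit on its preferred route. The oral qualifier may also simply name the scale on which 40°C is meant. Both readings are reasonable. Neither tells an investigator what to do with a permitted non-oral reading above 40°C, since the Protocol gives no equivalent limit and does not require an oral check. In Section 7.1.1, where any route was meant to count, the Protocol says so.

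The second defence is that other safeguards surround the case, and this largely stands. A severe solicited event in the first 7 days prompts contact with the site (Section 8.4.2), where an oral re-measurement is possible. Section 10.3.2 item g allows an important medical event to be classed as serious: "Medical or scientific judgement should be exercised in deciding whether reporting is appropriate in other situations". Item c says that doubt about hospitalization is resolved toward serious. Immediate safety concerns go to the sponsor (Section 8). Dosing after the first 30 women needs written authorization (Sections 8.2.3.1 and 8.2.3.2). The blinded safety review team reviews safety data throughout, and the IDMC receives unblinded reports about monthly and may recommend a hold outside the rules (Sections 8.2.3.3.2 and 8.2.3.3.3). A reader might infer that such a fever would go unanswered. The Protocol does not support that. What is lost is the automatic character of the stop.

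A reader might also infer that the Study Procedures Manual cannot contain route guidance, because Section 8 states: "The SPM provides the investigator and site personnel with administrative and detailed technical information that does not impact subject safety". That inference fails. The Protocol itself refers safety limits to the manual, including the laboratory grading for rule 2c (Table 18, footnote 2), the laboratory exclusions (Section 5.2.1.1) and the laboratory ranges for delaying vaccination (Section 7.1.1). Whether the manual addresses temperature route is unknown.

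**Conclusion.** The point holds in a narrow form, as a minor defect in the wording of a safety rule. Read literally, an isolated non-oral reading above 40°C in Days 1 to 7, without hospitalization, a judgement of seriousness or withdrawal, does not trigger the single-subject hold. Any response then rests on judgement (the investigator's, the sponsor's, the safety review team's or the IDMC's) or on a multi-subject rule that cannot respond to one case.

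The practical effect is probably small and cannot be quantified from the Protocol. The conclusion assumes that the oral qualifier is applied as written and that no route guidance exists in documents outside the Protocol. Sample size, endpoints and analyses are untouched.

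**What to change.** In Table 17, rule 1d, replace the oral qualifier so that a fever above 40°C counts "regardless of the location of measurement", and add two clauses. First, a non-oral reading above 40°C counts unless an oral re-measurement, taken immediately and before any antipyretic, is 40°C or below. Second, an oral reading above 40°C always counts. The second clause matters because an exception open to every reading could cancel a hold that an initial oral value had properly triggered.

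The edit is one entry in one table. Its downside is an occasional extra hold when a non-oral reading cannot be checked orally in time. A hold is not trivial: under Section 8.2.3.3.1 the allocation system is blocked, all dosing sites and the regulators are informed, the IDMC and the sponsor's safety board review the case, and a substantial amendment may be needed before restart. Confining the exception to unconfirmed non-oral readings keeps that cost small. If the sponsor does intend an oral-only limit, the rule should say so and state how a non-oral reading above 40°C is to be handled.
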